### **9.1.1 Imaging Assessment for the Study**

Any additional imaging that may demonstrate tumor response or progression (including scans performed at unscheduled timepoints and/or at an outside institution) should be collected for RECIST 1.1 tumor assessment and reviewed.

#### **9.1.1.1 Efficacy Assessments using CT scan or MRI**

The imaging assessment schedule is provided in Table 9.1.1.1-1.

Baseline imaging is required within 28 days prior to first dose, including CT chest, CT/MRI abdomen, and pelvis (with contrast, unless contraindicated), plus any area that is being monitored.

Participants must have an MRI of the brain at screening. Participants with a history of brain metastasis should have surveillance MRI approximately every 12 weeks, or sooner if clinically indicated.

Tumor assessments should continue every 8 weeks ( $\pm$  1 week) from first dose for the first 12 months on treatment, then every 12 weeks ( $\pm$  1 week) until documented radiographic disease progression. CT chest and CT/MRI abdomen and pelvis (with contrast, unless contraindicated), plus any area that is being monitored. Use the same imaging method as was used at screening. After 3 years on study, tumor assessments for long-term survivors can be performed at a frequency per institutional guidelines or every 24 weeks based on NCCN surveillance guidelines.

In Part 1, an *additional planned optional CT scan is suggested at W5*, to guide tumor biopsy as needed and to support predicting tumor response based on early tumor growth characteristics using a mathematical tumor growth model.

For participants who discontinue study treatment for reasons other than radiographic PD, follow-up scans should continue to be performed according to the on-study assessment schedule until PD, withdrawal of consent, start of subsequent therapy, death, or lost to follow-up.

Participants who remain on therapy beyond initial progression, will have an assessment performed within 6 weeks to confirm progression (see [section 8.1.2](#)).

**Table 9.1.1.1-1: Imaging Assessment Schedule (Part 1 and Part 2)**

Study Day	Event Relative to Dosing	CT		Biopsy c
Part 1				
Screening a ■,c	pre-dose	X		X
Cycle 1 Day 15 (Week 3) ■	pre-dose			
Cycle 1 Day 29 (Week 5)	-	X e		X
Cycle 2 Day 15	pre-dose	X		

**Table 9.1.1.1-1: Imaging Assessment Schedule (Part 1 and Part 2)**

[figure not shown]
Study Day	Event Relative to Dosing	CT	Biopsy c
(Week 9)			
Every 8 weeks ( $\pm$ 1 week) from first dose, for first 12 months on treatment	-	X	
After 12 months on treatment, Every 12 weeks ( $\pm$ 1 week) until documented radiographic disease progression.	-	X	
Progression	-	X	X
Part 2			
Screening a , c	pre-dose	X	
Every 8 weeks ( $\pm$ 1 week) from first dose, for first 12 months on treatment	-	X	
After 12 months on treatment, Every 12 weeks ( $\pm$ 1 week) until documented radiographic disease progression. f	-	X	

a Screening assessments should be performed within 28 days of treatment assignment.

c At screening, a fresh biopsy will be taken prior to treatment.

e W5 optional CT Scan, to guide biopsy as needed and to support predicting the tumor response based on early tumor growth characteristics using a mathematical tumor growth model.

f After 3 years on study, tumor assessments for long-term survivors can be performed at a frequency per institutional guidelines or every 24 weeks based on NCCN surveillance guidelines.

## **9.2 Adverse Events**

The definitions of an AE or serious adverse event (SAE) can be found in [Appendix 3](#).

AEs will be reported by the participant (or, when appropriate, by a caregiver, surrogate, or the participant's legally authorized representative).

The investigator and any designees are responsible for detecting, documenting, and reporting events that meet the definition of an AE or SAE and remain responsible for following up AEs that are serious, considered related to the study treatment or the study, or that caused the participant to discontinue before completing the study.

### **Contacts for SAE reporting specified in Appendix 3.**

#### **9.2.1 Time Period and Frequency for Collecting AE and SAE Information**

The collection of non-serious AE information should begin at initiation of study treatment until 100 days after the last dose of study therapy, at the timepoints specified in the Schedule of Activities (Section 2). Non-serious AE information should also be collected from the start of a

placebo lead-in period or other observational period intended to establish a baseline status for the participants.

Sections 5.6.1 and 5.6.2 in the Investigator Brochure (IB) represent the Reference Safety Information to determine expectedness of serious adverse events for expedited reporting. Following the participant's written consent to participate in the study, all SAEs, whether related or not related to study drug, must be collected, including those thought to be associated with protocol-specified procedures.

All SAEs must be collected that occur during the screening period and within 100 days of discontinuation of dosing. If applicable, SAEs must be collected that relate to any later protocol-specified procedure (e.g., a follow-up skin biopsy).

- The investigator must report any SAE that occurs after these time periods and that is believed to be related to study drug or protocol-specified procedure. Medical occurrences that begin before the start of study treatment but after obtaining informed consent will be recorded on the appropriate section of the eCRF section.
- All SAEs will be recorded and reported to Sponsor or designee within 24 hours, as indicated in [Appendix 3](#).
- The investigator will submit any updated SAE data to the sponsor within 24 hours of this being available.

For participants assigned to treatment and never treated with study drug, SAEs should be collected for 30 days from the date of treatment assignment.

Investigators are not obligated to actively seek AEs or SAEs in former study participants. However, if the investigator learns of any SAE, including a death, at any time after a participant has been discharged from the study, and he/she considers the event reasonably related to the study treatment or study participation, the investigator must promptly notify the sponsor.

The method of evaluating, and assessing causality of AEs and SAEs and the procedures for completing and reporting/transmitting SAE reports are provided in [Appendix 3](#).

### **9.2.2     *Method of Detecting AEs and SAEs***

Adverse events can be spontaneously reported or elicited during open-ended questioning, examination, or evaluation of a subject. (In order to prevent reporting bias, subjects should not be questioned regarding the specific occurrence of one or more AEs.)

### **9.2.3     *Follow-up of AEs and SAEs***

- Nonserious AEs should be followed to resolution or stabilization, or reported as SAEs if they become serious (see [Appendix 3](#)).
- Follow-up is also required for nonserious AEs that cause interruption or discontinuation of study treatment and for those present at the end of study treatment as appropriate.
- All identified nonserious AEs must be recorded and described on the nonserious AE page of the CRF (paper or electronic). Completion of supplemental CRFs may be requested for AEs and/or laboratory abnormalities that are reported/identified during the course of the study.

After the initial AE/SAE report, the investigator is required to proactively follow each participant at subsequent visits/contacts. All SAEs, and non-serious AEs of special interest (as defined in Section 9.2) will be followed until resolution, until the condition stabilizes, until the event is otherwise explained, or until the participant is lost to follow-up (as defined in Section 8.2).

Every adverse event must be assessed by the investigator with regard to whether it is considered immune-mediated. For events which are potentially immune-mediated, additional information will be collected on the participant's case report form.

Further information on follow-up procedures is given in Appendix 3.

#### **9.2.4 Regulatory Reporting Requirements for SAEs**

- Prompt notification by the investigator to the Sponsor of SAEs is essential so that legal obligations and ethical responsibilities towards the safety of participants and the safety of a product under clinical investigation are met.
- An investigator who receives an investigator safety report describing SAEs or other specific safety information (e.g., summary or listing of SAEs) from the Sponsor will file it along with the Investigator's Brochure and will notify the IRB/IEC, if appropriate according to local requirements.

Sponsor or designee will be reporting adverse events to regulatory authorities and ethics committees according to local applicable laws including European Directive 2001/20/EC and FDA Code of Federal Regulations 21 CFR Parts 312 and 320. A SUSAR (Suspected, Unexpected Serious Adverse Reaction) is a subset of SAEs and will be reported to the appropriate regulatory authorities and investigators following local and global guidelines and requirements.

#### **9.2.5 Pregnancy**

If, following initiation of the study treatment, it is subsequently discovered that a participant is pregnant or may have been pregnant at the time of study exposure, including during at least 5 half-lives after product administration, the investigator must immediately notify the BMS Medical Monitor/designee of this event and complete and forward a Pregnancy Surveillance Form to BMS designee within 24 hours of awareness of the event and in accordance with SAE reporting procedures described in Appendix 3.

In most cases, the study treatment will be permanently discontinued in an appropriate manner (e.g., dose tapering if necessary for participant safety). Please call the BMS Medical Monitor within 24 hours of awareness of the pregnancy.

Follow-up information regarding the course of the pregnancy, including perinatal and neonatal outcome and, where applicable, offspring information must be reported on the Pregnancy Surveillance Form.

Any pregnancy that occurs in a female partner of a male study participant should be reported to Sponsor or designee. In order for Sponsor or designee to collect any pregnancy surveillance information from the female partner, the female partner must sign an informed consent form for

disclosure of this information. Information on this pregnancy will be collected on the Pregnancy Surveillance Form.

### **9.2.6      *Laboratory Test Result Abnormalities***

The following laboratory test result abnormalities should be captured on the non-serious AE CRF page or SAE Report Form electronic, as appropriate. Paper forms are only intended as a back-up option when the electronic system is not functioning.

- Any laboratory test result that is clinically significant or meets the definition of an SAE
- Any laboratory test result abnormality that required the participant to have study treatment discontinued or interrupted
- Any laboratory test result abnormality that required the participant to receive specific corrective therapy

It is expected that wherever possible, the clinical rather than laboratory term would be used by the reporting investigator (e.g., anemia versus low hemoglobin value).

### **9.2.7      *Potential Drug Induced Liver Injury (DILI)***

Wherever possible, timely confirmation of initial liver-related laboratory abnormalities should occur prior to the reporting of a potential DILI event. All occurrences of potential DILIs, meeting the defined criteria, must be reported as SAEs (see [Section 9.2](#) and [Appendix 3](#) for reporting details).

Potential drug induced liver injury is defined as:

- 1) AT (ALT or AST) elevation > 3 times upper limit of normal (ULN), AND;
- 2) Total bilirubin > 2 times ULN, without initial findings of cholestasis (elevated serum alkaline phosphatase), AND;
- 3) No other immediately apparent possible causes of AT elevation and hyperbilirubinemia, including, but not limited to, viral hepatitis, pre-existing chronic or acute liver disease, or the administration of other drug(s) known to be hepatotoxic.

### **9.2.8      *Other Safety Considerations***

Any significant worsening noted during interim or final physical examinations, electrocardiogram, x-ray filming, any other potential safety assessment required or not required by protocol should also be recorded as a nonserious or serious AE, as appropriate, and reported accordingly.

#### **9.2.8.1    *Immune-mediated adverse events***

Immune-mediated adverse events (IMAE) are AEs consistent with an immune-mediated mechanism or immune-mediated component for which non-inflammatory etiologies (eg, infection or tumor progression) have been ruled out. IMAEs can include events with an alternate etiology which were exacerbated by the induction of autoimmunity. Information supporting the assessment will be collected on the subject's case report form.

### 9.3 Overdose

An overdose is defined as the accidental or intentional administration of any dose of a product that is considered both excessive and medically important. All occurrences of overdose must be reported as SAEs (see [Section 9.2](#)). In the event of an overdose the [investigator/treating physician] should:

- 1) Contact the Medical Monitor immediately.
- 2) Closely monitor the participant for AEs/SAEs and laboratory abnormalities.
- 3) Document the quantity of the excess dose as well as the duration of the overdosing in the CRF.

Decisions regarding dose interruptions or modifications will be made by the investigator in consultation with the Medical Monitor based on the clinical evaluation of the participant.

### 9.4 Safety

Planned time points for all safety assessments are listed in the Schedule of Activities. Safety assessments include AEs, physical examinations, vital signs, ECOG performance status, assessment of signs and symptoms, laboratory tests, and pregnancy tests as outlined in [Section 2](#).

#### 9.4.1 Clinical Safety Laboratory Assessments

- Investigators must document their review of each laboratory safety report.
- Screening laboratory assessments should be done locally within 14 days of first dose.
- On-study laboratory assessments should be done locally within 72 hours prior to each dose, as outlined in the Schedule of Activities in Section 2.
- Laboratory assessments should be performed locally at Follow-Up Visit 1, and should be repeated at Follow-Up Visit 2 if study related toxicity persists.

**Table 9.4.1-1: Laboratory Assessment Panels**

[figure not shown]
Hematology	
Hemoglobin	
Hematocrit	
Total leukocyte count, including differential	
Platelet count	
Chemistry	
Aspartate aminotransferase (AST)	Sodium
Alanine aminotransferase (ALT)	Potassium
Total bilirubin	Chloride
Alkaline phosphatase	Calcium
Lactate dehydrogenase (LDH)	Phosphorus
Creatinine	Lipase
Blood Urea Nitrogen (BUN) or Serum Urea Level	Amylase

[figure not shown]
**Table 9.4.1-1: Laboratory Assessment Panels**

[figure not shown]
Glucose	Magnesium
Albumin (screening only)	TSH, every 6 weeks (Free T3 and T4 performed at screening and reflex to free T3 and T4 if TSH is abnormal at subsequent timepoints) Creatinine clearance (CLcr)- screening only
Urinalysis (As clinically indicated)	
Protein	
Glucose	
Blood	
Leukocyte esterase	
Specific gravity	
pH	
Microscopic examination of the sediment if blood, protein or leukocytes esterase are positive on the dipstick	
Serology	
Serum for hepatitis C antibody or hepatitis C RNA, hepatitis B surface antigen, HIV-1 and -2 antibody (screening only) Testing for HIV must be performed at sites where mandated locally. See Appendix 8 .	
Other Analyses	
Pregnancy test (WOCBP only: as described in Section 2 .)	

#### **9.4.2 Imaging Safety Assessment**

Any incidental findings of potential clinical relevance that are not directly associated with the objectives of the protocol should be evaluated and handled by the Study Investigator as per standard medical/clinical judgment.

## 9.6 Biomarkers

The biomarker sampling schedule is provided in [Table 9.6-1](#) for Part 1 and in [Table 9.6-2](#) for Part 2.

**Part 1:** a biopsy should be taken during the screening period and up to 4-5 core biopsies are recommended at each tumor biopsy collection time point. An assessment of biopsy quality by a pathologist/cytopathologist is encouraged at the time of procedure. [REDACTED]

[REDACTED] Please refer to the lab manual for specific tumor collection instructions. Participants must have tissue submitted for PD-L1 IHC testing prior to the start of treatment. Samples should not be taken from target lesions. Samples will be sent to a third party to stain and score for PD-L1 expression using the PD-L1 IHC 28-8 pharmDx kit (Dako). Stained tissue samples will be assessed by a pathologist at a central lab identified by the Sponsor and scored as PD-L1 expressing if membrane staining is observed in  $\geq 1\%$  tumor cells among a minimum of 100 evaluable tumor cells.

An additional tumor biopsy will be collected at Cycle 1 Day 29 (Week 5) to evaluate potential pharmacodynamic biomarkers of response/safety to nivolumab + ipilimumab. Changes in candidate biomarkers at this time point may inform of early changes within the tumor microenvironment that contribute to efficacy. PD-L1 will be assessed in this on-treatment biopsy as indicated for the pre-treatment biopsy, above.

A tumor biopsy will be collected in subjects at progression. Changes in candidate biomarkers in this setting may inform of the mechanism(s) underlying acquired resistance and may inform of potential combination approaches to prevent/delay or reverse resistance. PD-L1 will be assessed in biopsy as indicated for the pre-treatment biopsy, above.

Collected tumors may be further analyzed by additional modalities, including, but limited to:

- IHC and/or cytometry (eg, flow-, chip- mass-spec based) to determine the abundance of immunoregulatory and other proteins such as [REDACTED] PD-L1, [REDACTED]  
[REDACTED]  
[REDACTED]
- [REDACTED]
- Genetic mutation detection methods;
- DNA and RNA sequencing (eg, whole exome/genome sequencing, whole transcriptome RNAseq and/or T-cell receptor sequencing);
- [REDACTED]  
[REDACTED]

[figure not shown]
The biomarker sampling schedule is provided in [Table 9.6-1](#) for Part 1.

[figure not shown]
**Table 9.6-1: Biomarker Assessment Schedule for Part 1**

[figure not shown]
Study Day	
Screening	
Cycle 1 Day1 (Week 1)	
Cycle 1 Day 29 (Week 5)	
Cycle 2 Day 15 (Week 9)	
Cycle 3 Day 1 (Week 13)	
Progression	

[figure not shown]
**Part 2** biomarker samples (blood and tumor tissue) for TMB analyses will be collected at screening. Fresh biopsy tissue is preferred for enrollment; follow lab manual for details. Archival tissue samples that are less than 3 months old may be submitted. For archival tissue, FFPE tissue block (preferred) or submission of 15 unstained tumor tissue sections for PDL-1 and TMB testing will be required. [REDACTED]

[REDACTED]

#### **9.6.10    *Tumor Mutational Burden Evaluation in Tissue and Blood Part 2***

Fresh biopsy is preferred or archival sample ( $\leq$  3 months old) are required for enrollment. For archival tissue, FFPE tissue block (preferred) or submission of 15 unstained tumor tissue sections for PDL-1 and TMB testing will be required. If fresh biopsy tissue is obtained, the collection of plasma/serum must be collected within 7 days.

Based on the Part 2 expansion cohort in this study, tumor TMB and blood TMB will be collected at baseline. The association of tissue and blood TMB analyses with clinical outcomes will be assessed independently.

#### **9.6.11    *Additional Research Collection***

Additional research collections and retention are mandatory for all subjects, except where prohibited by local laws or regulations. This protocol will include residual sample storage for additional research (AR).

This collection for additional research is intended to expand the translational R&D capability at Bristol-Myers Squibb, and will support as yet undefined research aims that will advance our understanding of disease and options for treatment. It may also be used to support health authority requests for analysis, and advancement of pharmacodiagnostic development to better target drugs to the right patients. This may also include genetic/genomic exploration aimed at exploring disease pathways, progression and response to treatment etc.

All requests for access to samples or data for additional research will be vetted through a diverse committee of the study sponsor's senior leaders in Research and Development to ensure the research supports appropriate and well-defined scientific research activities.

Samples will be securely stored by the BMS Biorepository in [REDACTED] or at a BMS approved third party storage management facility.

Samples will be stored in a coded fashion, and no researcher will have access to the key. The key is securely held by the Investigator at the clinical site, so there is no direct ability for a researcher to connect a sample to a specific individual.

Additional research samples will be retained for 15 years or the maximum allowed by applicable law. No additional sampling is required for residual collections.

Further details of sample collection and processing will be provided to the site in the procedure manual.

**Table 9.6.11-1: Residual Sample Retention for Additional Research Schedule**

Sample Type	Timepoints for which residual samples will be retained
All	All samples

## **9.7 Medical Resource Utilization and Health Economics**

Health Economics/Medical Resource Utilization and Health Economics parameters will not be evaluated in this study.

## **10 STATISTICAL CONSIDERATIONS**

[figure not shown]
### **10.1 Sample Size Determination**

**Part 1:** The planned sample size is approximately 100. Approximately up to 150 participants are expected to be enrolled to achieve 100 treated participants in the trial. For this hypothesis generating study, the sample size is mainly decided by operational feasibility, and sample size calculation is provided to illustrate the design characteristics of the study. Biomarker hypotheses generated from the study will be validated by analyzing data from other ongoing trials or data from future trials.

One of the co-primary objectives is to evaluate tumor mutational burden as a candidate biomarker of clinical efficacy of nivolumab and ipilimumab combination therapy. For this co-primary objective, the primary endpoint that will be used to measure clinical efficacy is objective response rate (ORR). [REDACTED]

One of the co-primary objectives of the study is to investigate the potential association between candidate biomarkers in peripheral blood and tumor tissue at baseline and on-treatment with clinical efficacy measures. For this co-primary objective, the primary endpoint that will be used to measure clinical efficacy is objective response rate (ORR). Patients can be divided into sub-groups by candidate biomarkers. No formal hypothesis testing will be conducted on ORR in overall patient population or in patient sub-groups. However, to evaluate the association between candidate biomarkers with ORR while factoring in the correlation among biomarkers, a multiple logistic regression or a penalized regression method (Elastic Net, implemented in SAS procedure GLMSELECT) may be used to select important biomarkers simultaneously. More specifically,

patient sub-groups can be identified by biomarkers as covariates in the model, and an important sub-group can be chosen based on biomarker effects estimated from the model. For example, the risk of each patient can be calculated based on estimated covariates, and a suitable cutoff point of patient level risk can be used to identify sub-groups of interest. Other methods can be used to define sub-groups. No matter what methods are used, scientific rationales need to be provided to support the patient sub-groups defined. For patient sub-groups identified, ORR and the associated confidence interval will be calculated, and the estimation bias due to selection bias will be adjusted by re-sampling method.

Although no formal hypothesis testing will be performed, the operating characteristics can also be illustrated in the hypothesis testing framework.

The power calculation was conducted in EAST 6 using Wald test statistics, and the null response rate of 0.23 was chosen based on data from LUX-Lung 3 and 6 study.

**Part 2:** The planned sample size is approximately 150 participants. Approximately 200 participants are expected to be enrolled to achieve 150 treated participants.

In study CA209568, a TMB analysis determined a TMB cutpoint that subjects at or above the cutpoint were predicted to experience therapeutic benefit from nivolumab in combination with ipilimumab. An exploration will be done for Part 2 subjects to confirm the cutpoint identified in CA209568. Within the TMB-evaluable subjects, it is expected that approximately 1/3 of those providing TMB will be categorized as being above the cutpoint, ie, [REDACTED]

[REDACTED] Table 10.1-1 presents the exact 95% CIs for some of the plausible scenarios of observed ORRs for TMB cutpoint positive (TMB+) participants in Part 2 based on blood TMB, as well as TMB based on tumor tissue.

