**Table 4-2: Objectives and Endpoints for Part 2.**

Objectives	Endpoints
Primary	

To evaluate the association between baseline tissue TMB/bTMB and clinical efficacy (ORR) for participants in Part 2

	

The clinical efficacy will be measured by the analysis endpoint of objective response rate (ORR). The association of ORR with baseline tissue TMB and bTMB will be assessed

Secondary	

To investigate bacterially generated and human components enteric biomarkers and identify potential associations with clinical outcomes, including safety and efficacy for participants

	

ORR, PFS, OS

Incidence of AES, SAEs, and select AEs

- Objective response rate (ORR):** The proportion of patients with best overall response (BOR) of RECIST 1.1 defined confirmed complete response (CR) or partial response (PR) in a pre-defined study population.
- Disease control rate (DCR):** The proportion of patients with best overall response (BOR) of RECIST 1.1 defined complete response (CR), partial response (PR), or stable disease (SD) in a pre-defined study population
- Duration of response (DOR):** DOR is defined as the time between the date of the first confirmed response (CR/PR) to the date of the first documented tumor progression (per RECIST 1.1) or death due to any cause. Participants who neither progress nor die will be censored on the date of their last evaluable tumor assessment. Participants who started any subsequent anti-cancer therapy without a prior reported progression will be censored at the last evaluable tumor assessment prior to or on the date of initiation of subsequent anti-cancer therapy.

- **Time to response (TTR):** TTR is measured from the time of first dosing date to the time the criteria for CR/PR are first met.
- **Progression free survival (PFS):** PFS is defined as the time from first dosing date to the date of the first documented tumor progression (per RECIST) or death due to any causes. Participants who neither progress nor die will be censored on the date of their last evaluable tumor assessment. Participants who started any subsequent anti-cancer therapy without a prior reported progression will be censored at the last evaluable tumor assessment prior to or on the date of initiation of subsequent anti-cancer therapy.

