### 10.3 Statistical and Computational Analyses

The association between ORR and tumor mutational burden will be explored using logistic regression model among treated patients evaluable for tumor mutational burden.

Due to limited participants as compared with the number of biomarkers that will be evaluated for the second co-primary objective, a multiple logistic regression model, or penalized regression methods (Elastic Net, implemented in SAS procedure GLMSELECT) will be used to assess the potential association between candidate biomarkers in peripheral blood and tumor tissue at baseline and on-treatment with clinical efficacy measures. The primary endpoint will be ORR, and other clinical efficacy measures will be analyzed as part of the secondary endpoints.

The analysis of the primary endpoint ORR will take place after the last treated subject is followed for [REDACTED]. Additional survival analysis will be conducted with longer follow up.

The statistical analysis plan will be developed and finalized before database lock and will describe the selection of participants to be included in the analyses, and procedures for accounting for missing, unused, and spurious data. Below is a summary of planned statistical analyses of the primary and secondary endpoints.

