### 10.3.1 Efficacy Analyses

Endpoint	Analysis Methods
Primary:	
ORR	
In Part 1, logistic regression model and ROC analysis will be used to evaluate tumor mutational burden as a candidate biomarker of ORR of nivolumab and ipilimumab combination therapy.
 
Multiple logistic regression or penalized regression will be used to screen for (baseline and post baseline) biomarkers simultaneously
 
ORR will be calculated for sub-groups identified by logistic or penalized regression methods, and the confidence interval by Clopper-Pearson method will be provided
 
In Part 2, ROC analysis will be used to confirm cutoffs for baseline tissue TMB and blood TMB that identify subjects who will experience therapeutic benefit based on ORR. Logistic regression will be conducted.
 
ORR will be calculated for TMB (tissue and blood) sub-groups and the confidence interval by Clopper-Pearson method will be provided.

Secondary	
DCR, DOR, TTR, PFS, and OS	
The analysis conducted for ORR will be repeated for other efficacy endpoints of interest. For PFS, OS and DOR, for selected patient sub-groups, Kaplan-Meier curves will be provided, and median of time to events and the associated confidence interval will be calculated.
 
Descriptive summary statistics of TTR will be provided for patients with a BOR of CR or PR.

Exploratory	

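### Sections 10.1 and 10.3 assign the elastic net for a yes/no endpoint to a linear-model procedure and leave the scale of patient risk undefined

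*Combined protocol and SAP*

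**What the plan says.** The endpoint is binary for each patient. The definitions under Table 4-2 give ORR as "The proportion of patients with best overall response (BOR) of RECIST 1.1 defined confirmed complete response (CR) or partial response (PR"), and section 10.1 applies it to the biomarker objective: "For this co-primary objective, the primary endpoint that will be used to measure clinical efficacy is objective response rate (ORR").

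For that objective, section 10.1 names two model families in one sentence, "a multiple logistic regression or a penalized regression method (Elastic Net", and gives the second a software implementation and a purpose: "implemented in SAS procedure GLMSELECT) may be used to select important biomarkers simultaneously". Section 10.3 names the same pair in firmer terms: "implemented in SAS procedure GLMSELECT) will be used to assess the potential association between candidate biomarkers". The reason it gives is that patients are few relative to the number of biomarkers. The methods table in section 10.3.1 again offers logistic or penalised regression, without naming a procedure.

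Section 10.1 then gives one example of how subgroups might be formed: "the risk of each patient can be calculated based on estimated covariates, and a suitable cutoff point of patient level risk can be used". It allows other ways of forming them and promises a resampling adjustment for selection bias. In section 10.3.1, "ORR will be calculated for sub-groups identified by logistic or penalized regression methods", with Clopper-Pearson intervals.

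**The concern.** GLMSELECT selects among general linear models by squared-error loss and has no binomial option. The protocol does not say this; it is a general property of the procedure the protocol names, and the sponsor's statistician can confirm it directly. On that footing, the two options in the sentence are different models on different scales. Logistic regression models the log-odds of response, while an elastic net in GLMSELECT fits the 0/1 outcome as if it were a continuous measurement. No likelihood or link is given for the penalised model, and no scale for the patient risk.

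Two things are at stake. The penalised step exists to select markers that will be carried to other trials for validation, and the loss function influences which markers are kept. Also, if patient risk is read off the linear fit, some values cannot be probabilities.

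**Working it through.** The plan gives no figure on this point, so there is none to reproduce. The check has two parts.

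**1. Is the penalised route likely to be used?** Section 10.1 plans about 100 treated patients in Part 1. Section 3.2.2 cites confirmed response rates of 39% to 47% in cohorts P and Q of CA209012. That implies about 100 × 0.39 = 39 to 100 × 0.47 = 47 responders. With many candidate markers and so few responders, unpenalised multiple logistic regression is unstable, so section 10.3's own rationale points towards the elastic net.

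**2. How much does the loss function matter?** Both fits use the penalty λ[α Σ|b| + (1 − α)/2 Σ b²] with α = 0.5, and differ only in the loss, where η = b0 + x′b:

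- squared error: (1/2n) Σ (y − η)², with fitted value η, which has no bounds;
- binomial: −(1/n) Σ [y η − log(1 + e^η)], with fitted value 1/(1 + e^−η), which always lies between 0 and 1.

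From the protocol: n = 100 and a response rate of 0.39. Assumed: n = 60 as a case with incomplete biomarker data; 20 or 50 markers with pairwise correlation 0.3; four true effects of moderate or large size on the log-odds scale; λ of 0.02, 0.05 or 0.10, the same nominal value for both losses. That gives 2 × 2 × 2 × 3 = 24 settings, with 30 simulated data sets each. The table shows the lowest and highest setting averages.

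| Quantity | n = 60 | n = 100 |
|---|---|---|
| Patients with squared-error fit below 0 or above 1 | 0.9% to 18.6% | 0.3% to 13.4% |
| Data sets with at least one such patient | 33% to 100% | 17% to 100% |
| Spearman correlation of the two patient rankings | 0.974 to 0.995 | 0.987 to 0.997 |
| Same side of a median cut | 95.7% to 97.9% | 96.0% to 98.1% |
| Jaccard overlap of selected markers | 0.75 to 0.93 | 0.83 to 0.95 |

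Across all settings, a median cut reassigns 100 − 98.1 = 1.9% to 100 − 95.7 = 4.3% of patients.

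Two further simulations tuned the penalty by 5-fold cross-validation (100 patients, 20 markers of which 8 skewed, 4 true, response rate about 40%, 60 data sets each):

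- The first had out-of-range values in 80% of data sets (about 3% of patients). Root mean squared error of predicted risk was 0.170 for squared error against 0.155 for the binomial fit: (0.170 − 0.155)/0.155 = 9.7% larger.
- The second had them in 70% of data sets (2.4% of patients), with errors of 0.172 against 0.165: (0.172 − 0.165)/0.165 = 4.2% larger. Jaccard overlap was 0.83. About 2.5% of patients changed subgroup at a top-third, 0.5 or 0.7 cut.

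**The case against.** A reader might infer that the subgroups will be built from impossible probabilities and that the reported response rates are therefore unsound. The documents do not support this, for four reasons:

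- The risk step in section 10.1 is only an example, other methods are allowed, and the risk is neither called a probability nor tied to GLMSELECT output. Screening in GLMSELECT and then computing risk from a logistic fit would be consistent with the text.
- Logistic regression is an equal alternative in sections 10.1, 10.3 and 10.3.1, and section 10.1 makes the penalised method optional.
- A cutoff needs only an ordering of patients, and the ordering barely changes.
- Subgroup ORR is an observed proportion with an exact interval, so it does not depend on fitted values being valid probabilities.

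A reader might also infer that a linear fit is least accurate where the cut would fall. Section 10.1 does not say where the cut falls, and the simulations measured overall error, not error at the extremes.

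All of this stands. It is also true that no hypothesis is formally tested, that biomarker hypotheses will be validated elsewhere, and that section 10.3 defers detail to an analysis plan due before database lock. None of it removes the mismatch: the only software named for the elastic net does not suit the endpoint, it is named in two sections, and no logistic refit is mentioned.

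**Conclusion.** The point holds as a mismatch between method and endpoint, of low to moderate importance. If the penalised route is run as written, the yes/no response is treated as continuous. Any patient risk taken from that fit can fall outside 0 to 1 (0.3% to 18.6% of patients on average across the 24 assumed settings), and the selected marker set differs somewhat from that of a logistic elastic net (Jaccard 0.75 to 0.95). The second effect deserves more attention, since selection is the stated purpose of the step. Cut-based subgroups change little, the subgroup response rates and their intervals are not invalidated, and no sample size or precision figure in the protocol changes.

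This rests on the known behaviour of GLMSELECT and on assumed marker numbers, correlations, effects and penalties. The 24 settings generated response from a logistic model, which favours the binomial fit, and the gain in risk accuracy (4% to 10%) should be read as specific to its assumed scenarios.

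**What to change.** In sections 10.1 and 10.3, replace the GLMSELECT implementation with an elastic net that uses a binomial likelihood with logit link, in software that supports it, and choose the penalty by cross-validated deviance. Define patient risk as the predicted probability from that model.

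A lesser option is to keep GLMSELECT, state that it is used for screening only, and state that patient risk comes from a logistic refit on the selected markers. This gives risks between 0 and 1 but leaves selection resting on squared error.

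Under either option, write that marker selection, penalty tuning and the choice of risk cut are all repeated inside each resample of the bias adjustment that section 10.1 already promises.

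The cost is a change of text and software before database lock. No extra patients, samples or visits are needed.
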